Effect of Blood Flow Restricted Exercise on Acute Systemic Irisin, Myostatin and Decorin Levels

Document date: 10/04/2022

The aim of the study is to measure and compare acute systemic irisin, myostatin and decorin levels after a single session of blood flow restricted resistance exercise and resistance exercise without blood flow restriction in healthy, trained male participants aged 18-35 years. For this purpose, a total of 22 people will be included in the study. Participants will be randomly allocated to 2 exercise groups as resistance exercise with blood flow restriction (BFR-RE) and

resistance exercise without blood flow restriction (HL-RE) and will be subjected to cross-over. In the HL-RE intervention, the exercise will be performed with a loading of 80% of 1 RM, with 4 sets x 7 repetitions, with 60 seconds of rest between sets. In the BFR-RE intervention, the exercise will be done as a set of 30 repetitions with a loading of 30% of 1 RM and an additional 3 sets x 15 repetitions, with 30 seconds rest between sets. Total exercise volumes were tried to be equalized and skeletal muscle hypertrophy was selected in accordance with exercise guidelines. In both groups, bilateral leg extension exercise will be performed using the leg extension tool for resistance exercise. In the blood flow restriction group (BFR-RE), the cuff will be placed in the proximal region of the thigh bilaterally, inflated to a pressure equivalent to 50% of the estimated arterial occlusion pressure (AOP), and leg extension exercise will be performed under this condition. In the BFR-RE group, the blood flow restriction time will be between 5-10 minutes. Exercise sessions will be conducted under supervision. Venous blood samples will be collected from the arm antecubital region of the participants just before the exercise session, immediately after the exercise, and 1 hour after the exercise. Plasma irisin, myostatin and decorin levels will be measured from the samples taken. It is well known that resistance exercise is important in maintaining and increasing muscle mass (hypertrophy). Studies have shown the involvement of certain myokines in skeletal muscle hypertrophy, although few studies have been conducted on the systemic response of myokines to BFR-RE that may play a potential role in hypertrophy. Therefore, the planned study aimed to reveal the similarities or differences in the systemic myokine response between BFR-RE and HL-RE.

22 male participants between the ages of 18-35 will be included in the study. Participants must have been doing resistance exercises for at least one year. In the study, plasma irisin, myostatin and decorin myokine levels will be measured from venous blood samples to be taken from the participants. Sample size was analyzed using 2-group repeated measures (three time points for each period) crossover design, single-factor, repeated measure methodology (repeated measure anova). A sample of 19 athletes measured at 6 time points reaches 80% power to detect differences between averages using the F-Test at a significance level of 0.05. The effect size was set as $f = 0.25$ (medium) and the correlation between measurements was taken as 0.5. The accepted sample size for equal group size is 20. Considering loss of follow-up or non-compliance with the experiment, the final sample size was 22 with a 10% attrition rate.

A randomization algorithm (Maximum Allowed % Deviation = 10%) was applied using PASS software 11.0 (NCSS LLC, Kaysville, UT) to generate a randomization list that would allow participants to be assigned to two groups of 11 each.

The parameters to be examined in statistical analyzes are plasma irisin, myostatin and decorin levels. Statistical analyzes IBM SPSS Statistics 25.0 (IBM SPSS Statistics for Windows, Version 25.0. Armonk, NY: IBM Corp.) package program and R 3.5.3 software (R software, version 3.5.3, R Foundation for Statistical Computing, Vienna, Austria ; <http://r-project.org>). Significance level was determined as 0.05 in all analyzes. Time group interaction will be analyzed at a significance level of 0.1. In the study, numerical data will be summarized with mean, standard deviation, median, minimum and maximum values, and categorical data will be summarized using frequency and ratio values. The assumption of normality in numerical variables will be checked with the Shapiro Wilk test at each group and time point, and in parallel with the results, the time-dependent change in the groups will be analyzed

parametrically with the linear mixed model (linear mixed model) or non-parametrically with the Brunner-Langer model. If the interaction is found to be significant, subgroup analyses will be made, both within and between groups. Bonferroni correction will be used for multiple comparisons. Qualitative variables will be analyzed with Pearson Chi-square test, while all quantitative demographic data between groups will be analyzed with independent group ANOVA or Kruskal-Wallis test.

Study Protocol:

- Informing the participants about the study and obtaining their consent.
- Recording the demographic information of the participants.
- Making anthropometric measurements before the interventions, filling out the EGZ-A+ questionnaire, calculating HRR, making 1RM and AOP measurements.
- Exercise interventions will be done at the same times of the day and at 1 week intervals.
- Before the exercise interventions, warm-up on the bicycle ergometer at 50% of the HRR for 10 minutes, followed by lower extremity stretches.
- In the HL-RE intervention, the exercise will be performed with 4 sets x 7 repetitions, with a 60-second rest between sets, with the load on the knee extension device being 80% of 1 RM. Venous blood samples will be taken immediately before exercise, immediately after exercise, and 1 hour after exercise.
- In the BFR-RE intervention, the cuff will be placed in the proximal thigh region and inflated with the help of the cuff to the pressure corresponding to 50% of the AOP, and the exercise will be performed under this condition. The exercise will be performed as a set of 30 repetitions with a load of 30% of 1 RM on the knee extension device and an additional 3 sets x 15 repetitions, with 30 seconds rest between sets. Venous blood samples will be taken immediately before exercise, immediately after exercise, and 1 hour after exercise.
- In order to increase the comfort of the participant, blood samples will be collected by experienced people through a vein to be opened in the arm antecubital region.

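### Session order is randomised, but the analysis text specifies no period term: any difference between sessions 1 and 2 costs power and, if the two orders finish unequally, can bias the BFR-RE versus HL-RE contrast

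*Combined protocol and SAP*

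**What the plan says.** The opening design paragraph allocates participants at random to BFR-RE or HL-RE and adds that they "will be subjected to cross-over". The randomisation paragraph describes a list that allows "participants to be assigned to two groups of 11 each". The Study Protocol list adds: "Exercise interventions will be done at the same times of the day and at 1 week intervals". Since everyone does both regimens, the two groups of 11 are in effect the two session orders.

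The sample size paragraph reflects this: "Sample size was analyzed using 2-group repeated measures (three time points for each period) crossover design". It is the only place where the word period is used.

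The statistical analysis paragraph then says that "the time-dependent change in the groups will be analyzed" with a linear mixed model or, depending on the normality checks, a Brunner-Langer model. The interaction of time and group is tested at 0.1. If it is significant, follow-up comparisons are made inside and across the groups with Bonferroni correction. For baseline description, "all quantitative demographic data between groups will be analyzed with independent group ANOVA or Kruskal-Wallis test". No model equation, period term, sequence term or random-effect structure is given.

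**The concern.** The analysis text reads as if for a parallel-group trial. In a crossover each man is his own control, and the regimen effect is estimated from within-person differences. Those differences also contain whatever separates session 1 from session 2: adding it for one order and subtracting it for the other. If period is not in the model, two things follow.

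- With equal numbers in the two orders the session difference cancels from the estimate but stays in the residual, so power is lost.
- With unequal numbers it no longer cancels, and part of it enters the regimen contrast. The plan itself allows for 10% attrition.

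The Brunner-Langer alternative has a further gap: its layout depends on whether group is a between- or a within-participant factor, and the plan does not say.

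**Working it through.** **1. The plan's own figure.** Inputs from the sample size paragraph: 6 measurements, f = 0.25, correlation 0.5, alpha 0.05. With noncentrality f² × n × 6 / (1 − 0.5) on 5 and 5(n − 1) degrees of freedom:

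- n = 18: noncentrality 13.5, power 0.794
- n = 19: noncentrality 14.25, power 0.820

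So 19 reproduces. At n = 20, the plan's figure for equal groups, power is 0.843.

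**2. One within-person contrast.** Let s be the SD of a man's BFR-RE minus HL-RE difference, τ its true mean, and d the session-2-minus-session-1 difference in the same quantity. The documents give neither s nor d, so d is an assumed range in units of s. The expected difference is τ + d for those who do HL-RE first and τ − d for those who do BFR-RE first.

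With 10/10 completers the estimate is unbiased, but the standard error is inflated by √(1 + d² × 20/19). I set τ = 0.662s, which gives 80% power with period in the model (18 df, two-sided 5%). The simulated power of the unadjusted test (19 df) is:

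| d | SE inflation | Power with period | Power without |
|---|---|---|---|
| 0.25s | 1.03 | 80% | 78% |
| 0.5s | 1.12 | 80% | 72 to 73% |
| 0.75s | 1.26 | 80% | 63% |
| 1.0s | 1.43 | 80% | 50% |

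The unadjusted test is conservative: its true level at d = 0.5s is 2.9% for a nominal 5%. At d = 0, including period costs about 0.2 points (79.7% against 79.9%).

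*Scale of s.* Under the plan's correlation of 0.5, and with compound symmetry assumed, a level difference at one sample has s = √(2 × 0.5) = 1 measurement SD. A difference between two changes has s = √(4 × 0.5) = 1.41 SD. For changes, d = 0.25s is therefore 0.35 SD and d = 0.5s is 0.71 SD.

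**3. All six measurements.** Take one random intercept per participant, total SD 1 and residual variance 0.5, with a session shift π equal at all three samples. Omitting period inflates the residual variance by 1 + (6n × π²/4) / (0.5 × 5(n − 1)). At n = 20 and π = 0.5 this is 1 + 7.5/47.5 = 1.16. Power at n = 20, balanced, without period:

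| π (SD) | Variance inflation | Six-mean F-test (0.843 at π = 0) | Interaction at 0.10 (0.80 at π = 0) | Level contrast (0.80 at π = 0) |
|---|---|---|---|---|
| 0.25 | 1.04 | 0.825 | 0.786 | 0.789 |
| 0.5 | 1.16 | 0.770 | 0.749 | 0.755 |
| 0.75 | 1.36 | 0.664 | 0.682 | 0.698 |
| 1.0 | 1.63 | 0.513 | 0.588 | 0.617 |

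A random effect for session within participant would absorb a constant shift from the interaction test, but the plan specifies none.

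**4. Bias with unequal completion.** Bias = d × (n1 − n2)/(n1 + n2):

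- 11/11 or 10/10: 0
- 11/9: 2/20 = 0.10d
- 11/8: 3/19 = 0.16d

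With period in the model it is 0 in every case. As an example, take 11/9 completers, a 0.5 SD shift and a true level difference of 0.37 SD averaged over the samples. The estimate is 0.42 or 0.32 according to direction, and power is 0.87 or 0.64 instead of about 0.80.

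**5. Which contrasts are affected.** A shift equal at all three samples gave zero bias in the time-by-group interaction under every drop-out pattern tried. If instead the session changes the two post-exercise samples relative to the first, the interaction is biased by 0.10 times that change at 11/9.

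**The case against.** *No model is written out.* A linear mixed model can hold a period term, and the sample size text shows that the authors had periods in mind. This stands: a reader might infer that the plan excludes period, but the documents show only that none is specified. The omission is read from the terms that are named.

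*The gatekeeping test is largely protected from bias.* Follow-up comparisons depend on the interaction, and a constant session shift does not bias it. This also stands. A reader might infer that any session difference distorts the regimen comparison after drop-out. For the interaction that is true only of a difference that alters the time course.

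*The assumed range may be generous.* The men have trained for at least a year, 1RM and occlusion pressure are measured before the interventions, and sessions are at the same time of day. Each man exercises under the cuff only once, so getting used to it is not a clear session effect. Nothing in the documents makes a large d likely.

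*Imbalance may not occur.* If two of 22 drop out regardless of order, the chance of 10/10 is 11 × 11/231 = 52%, and of 11/9 it is 48%. The 11/8 case exceeds the planned attrition.

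*Sequence and carry-over.* Omitting sequence alone changes neither the bias nor the standard error of the within-person contrast materially. A period term does not remove carry-over that differs by regimen.

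These points limit the size of the problem. They offer no reason to leave period out.

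**Conclusion.** The point holds as a free improvement. The design randomises session order, and the analysis text specifies no term for it. The harm is modest if sessions differ little: 1 to 2 points of power at 0.25s, and a bias of one tenth of the session difference at 11/9. It becomes substantial only for session differences that the documents neither state nor make likely (power about 63% at 0.75s and 50% at 1.0s).

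A reader might go on to infer more false positives or a wrong sample size. Neither follows. With balanced orders the true level falls below nominal, and the stated 19 reproduces from its own inputs.

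The figures rest on an assumed d, on compound symmetry for the conversion to measurement SDs, and on a single random intercept for the six-measurement results.

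**What to change.** - **Linear mixed model:** state regimen, time, regimen-by-time, period and period-by-time as fixed effects, with random effects for participant and for session within participant. Sequence may be added by convention.
- **Brunner-Langer route:** treat regimen and time as within-participant factors and session order as the between-participant factor. The order-by-regimen term then carries the period effect and separates it from the regimen effect. A layout with regimen and time alone would still have no period factor.
- **Demographics:** describe them by session order. Across regimens the participants are the same people, so a between-regimen test has no meaning.

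The cost is SAP wording and about one degree of freedom per contrast, or about 0.2 power points if there is no period effect. No new data are needed, because session order is known from the randomisation list.
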